## Work calendar

Once the 3-month recruitment period has ended and the initial assessment tests have been completed, an 8-week rehabilitation program will begin with a subsequent 12-month follow-up from the start of the PRR. After this, the analysis, exploitation of the data and subsequent dissemination of the results will be carried out.

- **Data exploitation period:** once the recruitment period has ended, the collected data will be analyzed and exploited, with the aim of subsequently disseminating the results.

### **Potential practical applicability of the results**

The applicability of this project stems from the possibility of knowing the possible factors that may predispose to poor exercise tolerance and being able to take measures to improve this situation. In addition, determining if there is a relationship between effort tolerance and the severity of bronchiectasis according to the measurement scales could help us decide at what time to start a rehabilitation program. physical activity program, without this entailing additional economic costs. In addition, the development of the RR Program would provide an increase in exercise capacity and consequently an improvement in health-related quality of life, which would translate into a reduction in direct expenses such as hospitalizations or emergency visits (due to better control of exacerbations) or indirect, derived from social costs (due to the dependence and limitations of these patients in decompensation).

For all these reasons, the interest of the work extends to the entire health system to promote a sustainable method and improve exercise tolerance and fundamentally the quality of life of patients and survival.

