### Secondary

Assess the degree of baseline physical activity of patients with BE without CF and its changes after PR.

Know the severity through the prognostic scale E-FACED

Determine the impact of PR on health-related quality of life and anxious/depressive state, symptoms, exacerbations

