### Exclusion criteria

- Smokers or former smokers of less than 6 months or with a history of consumption of 15 packs/year.
  - Cystic fibrosis.
  - Active infections (bronchopulmonary aspergillosis, pulmonary tuberculosis).
  - Active tuberculosis.
  - poorly controlled asthma

- Chronic obstructive pulmonary disease.
- Diseases that prevent adequate performance of exercise (neuromuscular pathology or residual injuries)
- Medical diseases that put the individual at risk of a decompensation due to the performance of any physical activity or cardiopulmonary stress test (unstable ischemic heart disease, acute myocardial infarction less than 1 month).
- Pregnancy.
- Mental disorder that prevents the adequate interpretation of the indications or performance of the tests.

- **Study design.**

Prospective and randomized study with consecutive inclusion of patients from the Non-CF bronchiectasis BE monographic clinic of the Virgen Macarena Hospital (Seville). Patients who meet the inclusion criteria will be randomized into two groups: control and intervention, patients will be assigned to each group using a numerical sequence generated by computer until the sample size is obtained.

The control group will receive basic recommendations on physical activity and the intervention group will be included in a mixed respiratory rehabilitation program (combining home and hospital sessions).

**Visit 1:** inclusion of patients with BE who comply with inclusion. Signature of informed consent and randomization of patients.

**Visit 2:** All patients will undergo an initial assessment of the degree of physical activity by means of accelerometers (®Sensewear arm band) for 3 days including weekends, as well as pulmonary function and exercise tolerance tests, stratification of severity according to the E-FACED scales.

\* Control group: written recommendations on performing some physical activity for at least 30 minutes of moderate intensity according to the recommendations of the Spanish Society of Pulmonology and the Andalusian Society of Pulmonology and Thoracic Surgery. (Casilda Olveira, Costa, and Martínez-García 2016) , (C Olveira et al. 2010). A phone call every 15 days to assess the physical activity carried out without talking about exercise or physical activity.

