\* Intervention group: Patients will be included in an 8-week outpatient program with recall sessions led by our physiotherapist once every 2 weeks in the hospital's Respiratory Rehabilitation gym. In the first session, patients will be instructed on how to perform home exercises as well as how to use the Borg scale. A phone call weekly to provide support and general advice about exercise or physical activity.

The program will combine isotonic strength and resistance exercises. Resistance training will consist of bicycle or walking exercises (depending on the availability of each patient), with a progressive increase in distance or time of completion depending on symptom control.

The strength training program will include upper and lower limb exercises that will begin with no load and to which weights will be progressively added depending on the control of symptoms, in 2 sets of 6-8 repetitions:

- Hanger (to work the latissimus dorsi muscle).
- Butterfly (pectoralis major muscle work).
- Neck press (brachial triceps and deltoid work).
- Flexion of legs (work of biceps femoris and gastrocnemius).
- Extension of legs (work of quadriceps femoris): place a weight or ballast. Stretch the leg and raise the thigh
- Exercises with elastic bands: upper and lower limbs. Separate both ends of the tape as much as possible.
- Walking: increase the walking time progressively.
- Bicycle or treadmill: submaximal exercise. Constant pedaling at about 60 rpm with moderate intensity.

Patients will be encouraged to maintain the exercises after the study.

**Visits 3, 4 and 5:** at 8 weeks (time of completion of the rehabilitation programs), 6 months and 12 months, respectively. At the end-of-program and follow-up visits, all the measurements made at the baseline visit will be repeated, as well as the record of exacerbations.

All patients will receive an educational program about their disease as well as an individualized respiratory physiotherapy program including relaxation techniques, secretion management and assessment of nutritional status.

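### Exacerbations are the only clinical event recorded; exercise-related adverse events, admissions, emergency visits and reasons for withdrawal are not collected by arm

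*Combined protocol and SAP*

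**What the plan says.** Follow-up is defined in the Method section under Visits 3, 4 and 5 (8 weeks, 6 months and 12 months): "all the measurements made at the baseline visit will be repeated, as well as the record of exacerbations". The Secondary objectives name the outcomes of interest beyond exercise capacity, physical activity and severity: "Determine the impact of PR on health-related quality of life and anxious/depressive state, symptoms, exacerbations". Measurement methods and variables lists cycle ergometry, the 6-minute walk, accelerometry, two questionnaires, E-FACED, spirometry, demographics, comorbidities, smoking and dyspnoea. Statistical analysis contains no safety or healthcare-use analysis.

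Three other places bear on this:

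- **Exclusion criteria** rule out "Medical diseases that put the individual at risk of a decompensation due to the performance of any physical activity or cardiopulmonary stress test", with cardiac examples: "unstable ischemic heart disease, acute myocardial infarction less than 1 month".
- **Method, intervention group**, describes an 8-week programme with a physiotherapist-led hospital session once every 2 weeks, a weekly support call, and strength exercises that start unloaded and "to which weights will be progressively added depending on the control of symptoms".
- **Potential practical applicability of the results** expects a "reduction in direct expenses such as hospitalizations or emergency visits (due to better control of exacerbations") and extends the interest of the work to the whole health system.

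Control patients are called every 15 days, and the plan keeps exercise and physical activity out of the conversation on those calls.

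**The concern.** The plan recognises a hazard and expects a benefit, but has no data item for either. A chest-pain episode, faint, fall or muscle injury during home training has no place in the record. Nor does a cycle test cut short because of symptoms. An admission or emergency visit would be captured, if at all, only where it formed part of an exacerbation, and the content of that record is not specified.

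The same gap affects the reading of losses. Potential Job Limitations expects losses from unforeseeable decompensations, but no reason for leaving is recorded. If some programme patients stop because training caused them a problem, the analysed programme patients are a selected group, and nothing in the data would show it.

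These data cannot be recovered at analysis if they are not collected. A report could then show gains in exercise capacity for a home programme proposed for wider use, with no account of what it cost patients and no direct evidence on the admissions it is expected to prevent.

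**Working it through.** **1. What is expected or recognised, against what is recorded**

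| Item | Where the plan raises it | Data item in the available text |
|---|---|---|
| Decompensation from activity or stress test (cardiac examples) | Exclusion criteria | None |
| Fewer admissions and emergency visits | Practical applicability | None |
| Losses from decompensation | Potential Job Limitations; 15% in Statistical analysis | No reason recorded |
| Exacerbations | Secondary objectives | Yes, Visits 3, 4 and 5 |
| Symptoms, quality of life, lung function, exercise capacity | Objectives; variables | Yes, baseline and Visits 3, 4 and 5 |

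The first three rows are the gap. The last two show that respiratory and functional worsening is covered in both arms.

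**2. The plan's own figure.** The only sizing figure is 30 per group, with 95% power and 15% loss. No effect size or standard deviation is given, so it cannot be reproduced. It also concerns exercise capacity and physical activity, not events. It is used below only as the number of patients. Expected losses are 30 × 0.15 = 4.5 per group, which leaves 25.5; I use 25 as the lower case.

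**3. What event collection could show about harm in the programme arm**

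One-sided 95% upper limit after zero events: 1 − 0.05^(1/n).

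- n = 30 (all randomised): 1 − 0.05^(1/30) = 9.5%
- n = 25 (if those lost gave no information): 1 − 0.05^(1/25) = 11.3%

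Chance of seeing at least one event when the true per-patient risk is p: 1 − (1 − p)^n. The plan gives no event rates, so p is an assumed range.

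| p | n = 30 | n = 25 |
|---|---|---|
| 1% | 26.0% | 22.2% |
| 2% | 45.5% | 39.7% |
| 5% | 78.5% | 72.3% |
| 10% | 95.8% | 92.8% |

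Common harms would probably be seen. Rare ones could well be missed.

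**4. What it could show about admissions**

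Normal approximation for two proportions, two-sided 5%: power = Φ[(d − 1.96·se0)/se1], where d = p1 − p2, p̄ is the mean of p1 and p2, se0 = √(2p̄(1 − p̄)/n) and se1 = √((p1(1 − p1) + p2(1 − p2))/n). The 12-month admission proportions are assumed.

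Example, 20% to 10% with n = 30: p̄ = 0.15, se0 = √0.0085 = 0.0922, se1 = √0.00833 = 0.0913. Then (0.10 − 0.1807)/0.0913 = −0.884, and power is 18.8%.

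| Control to programme | 30 per arm | 25 per arm | Analysed per arm for 80% power |
|---|---|---|---|
| 20% to 10% | 18.8% | 16.4% | 199 |
| 30% to 15% | 28.2% | 24.2% | 121 |
| 40% to 20% | 39.1% | 33.5% | 82 |
| 50% to 25% | 51.7% | 44.5% | 58 |

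Even a halving would usually not reach significance at this size.

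**The case against.** The plan has real safeguards. Patients at risk of decompensation are excluded, the first session teaches the exercises and the Borg scale, weights start at nothing, and a physiotherapist sees patients every 2 weeks with a call each week. These reduce risk, but they do not record what happens.

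Four stronger readings are tempting, and the documents do not support them:

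- **That the plan names injury as a risk of training.** Residual injuries appear in the exclusion criteria only as an existing barrier to exercise. The risk named is decompensation, with cardiac examples.
- **That the trial cannot detect harm at all.** Exacerbations, symptoms, quality of life, lung function and exercise capacity are measured in both arms up to 12 months.
- **That the trial fails to test one of its endpoints.** The statement on admissions is an applicability rationale, not an objective. It works through exacerbation control, and exacerbations are recorded, so part of the pathway is observable.
- **That admissions are certainly recorded nowhere.** The exacerbation record is unspecified and might capture hospital-treated episodes. It would still not be a count of admissions from all causes.

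Two further objections shape the remedy. Asking control patients on the telephone whether an event was related to exercise would breach the plan's restriction on those calls. And collection alone would not settle the claim about admissions, as the power table shows. Both stand, and the fix allows for them.

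**Conclusion.** The point holds in a limited form. In the text available for review, exacerbation is the only clinical event recorded. The plan cannot describe non-respiratory harm or healthcare use by arm, and cannot tell harm-related withdrawals from the 4 to 5 losses per group that it expects.

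The primary comparison of exercise capacity can still be made, so this is a recommended change and not a fatal fault. The gain is modest but real: an upper limit of 9.5% after no events in 30, where the plan now yields no bound. That limit assumes the outcome is known for every randomised programme patient; with 25 known it is 11.3%. The limits follow from the sample size alone and say nothing about how likely harm is. The power range of about 19% to 52% rests on assumed admission proportions of 20% to 50%, halved, with 30 analysed per arm.

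**What to change.** - **Event form.** Add a short form to the record at Visits 3, 4 and 5, and to calls at the same 15-day interval in both arms. Ask neutrally about hospital admission or emergency visit with cause, chest pain, syncope, fall and musculoskeletal injury. Do not ask at every weekly programme call, because more frequent questioning would find more events in that arm.
- **Relation to exercise.** Record this at the visits and not on the control calls, so that the restriction on those calls is kept.
- **Tests and withdrawals.** Record any exercise test stopped early and why, and the reason for each withdrawal.
- **Call period.** State how long calls continue in each arm; the plan gives no duration for the control calls. Where calls have ended, the visits carry the collection, with recall of up to 6 months.
- **Analysis.** Add a descriptive table by arm for all randomised patients, with confidence intervals and no claim from significance tests.
- **Wording.** Restate the expectation on admissions and emergency visits as a hypothesis.

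The cost is one form and one table on contacts already planned, with slightly longer calls and visits. No visits or procedures are added.

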### **Facilities and techniques already available for the project**

We have a Pulmonary Function Laboratory of the Pneumology UGC of the HUV Macarena where cycle ergometry and pulmonary function tests will be carried out, in addition to the space set aside for carrying out the 6-minute walk test.

The recruitment of Non-CF Bronchiectasis patients will be carried out in the specialized bronchiectasis clinic of the Virgen Macarena Hospital. We also have research support staff; aimed at the initial assessment of patients, signing the consent, help with questions about the questionnaires and diagnostic tests.
